5.6.1 Tumor Tissue Specimen

Pre-treatment tumor tissue specimens in the form of a paraffin embedded block or a minimum of 10 unstained slides will be submitted for central PD-L1 immunohistochemistry (IHC) assessment prior to randomization. These biopsy samples should be excisional, incisional, punch or core needle. Fine needle aspirates or other cytology specimens are insufficient for downstream biomarker analyses. PD-L1 stained tissue sections will be assessed by a pathologist and scored as PD-L1 expression $\geq 5\%$ or PD-L1 expression $< 5\%$ based on the frequency of tumor cell surface PD-L1 staining among a minimum of a hundred (100) evaluable tumor cells. Where membrane staining is obscured by high cytoplasmic staining or melanin content, but the tumor tissue sample contain the minimum number of evaluable tumor cells, samples will be deemed PD-L1 indeterminate.

Tumor samples will be stained for PD-L1 by ICH and the stained tissue sections will be assessed by a pathologist for tumor and immune cell membrane expression of PD-L1. These tumor samples may also be assessed for the expression of other immune or melanoma related genes, RNAs and/or proteins, as well as, the presence of immune cell populations using a variety of methodologies inclusive of, but not limited to IHC, qRT-PCR, genetic mutation detection, fluorescent in-situ hybridization (FISH) and exome sequencing. Various molecular markers with potential predictive value for the treatment of melanoma with nivolumab, ipilimumab and other immunotherapies are currently under investigation and may be assessed in this study. These tumor tissue biomarkers include, but are not limited to PD-1, PD-L2, tumor infiltrating lymphocytes (TILs) or subpopulations of TILs and a Th1 immune mRNA expression signature. In addition, other methods of measuring tumor PD-L1 expression may also be assessed.

Tumor tissue samples may also be collected upon progression. This sample may be used for the assessment of markers implicated in resistance to immunotherapeutic agents, including but not limited to other T cell checkpoint receptors and ligands (eg, Lag-3, Tim-3) and intratumoral immune cell subsets, including but not limited to, T regulatory cells and myeloid derived suppressor cells. These samples may also be used to investigate the effect of nivolumab + ipilimumab on the expression of potentially relevant predictive and/or prognostic melanoma biomarkers, including, but not limited to PD-L1. Both the pre-treatment tumor sample

and the sample collected upon recurrence may be retrospectively assessed for BRAF mutation status, as well as for the expression of other immune or melanoma related genes.

5.6.3 Peripheral Blood Mononuclear Cells (PBMCs)

Peripheral blood samples will be taken prior to initiation of study therapy and at designated timepoints on-treatment (see Section 5.1 for additional details on the blood sample collection schedule) for PBMC preparation, except at sites where the stability of the samples after shipment to the Central Laboratory cannot be guaranteed. Samples must be shipped within 48 hours to a BMS-designated central laboratory for processing.

These PBMC samples may be used for immunophenotyping or characterization of the immune cell subsets in the periphery, including, but not limited to, T cells, B cells, NK cells, or subpopulations of the aforementioned immune cell types. These samples may also be used to assess immune cell function or antigen specific T cell proliferation or activation pending emerging information from other nivolumab or ipilimumab studies.

5.6.4 Whole Blood for SNP Assessment

Whole blood samples for exploratory pharmacogenetic assessment will be collected from all subjects and put in frozen storage. Genomic DNA will be extracted and subsequently assessed for single nucleotide polymorphisms (SNPs) and other genetic variations in genes that may predispose subjects to nivolumab or ipilimumab benefit or adverse events (unless restricted by local requirements.) Such genes include, but are not limited to PD-1, PD-L1, PD-L2 and CTLA-4. Additional use of these data may include correlative analyses aimed at identifying genotypic associations with clinically-relevant biomarkers identified by other methodologies described in this section.

5.6.5 Myeloid-Derived Suppressor cells

Myeloid derived suppressor cells (MDSCs) are an immune cell population capable of suppressing T cell activation and proliferation. Low pre-treatment MDSC levels in peripheral blood may be associated with better overall survival in melanoma patients treated with the immunotherapeutic agent ipilimumab.²⁸ MDSCs will be measured at baseline and on-treatment to assess pharmacodynamic changes or associations with outcome (see Section 5.6.3 for additional details on the blood sample collection schedule).

5.7 Outcomes Research Assessments

HRQoL will be assessed using the EORTC QLQ-C30. The EORTC QLQ-C30 is the most commonly used QoL instrument in advanced melanoma clinical studies. It is a 30-item instrument that has gained wide acceptance in oncology clinical studies. The EORTC QLQ-C30 comprises 6 functional scales (physical functioning, cognitive functioning, emotional functioning, social functioning and global quality of life) as well as nine symptom scales (fatigue, pain, nausea/vomiting, dyspnea, insomnia, appetite loss, constipation, diarrhea, and financial difficulties). Except for the overall health status and global quality of life items, responses for all items are 4-point categorical scales ranging from 0 (Not at all) to 4 (Very much). The overall health status/quality of life responses are 7-point Likert scales.

General health status will be measured using the EQ-5D. The EQ-5D is a standardized instrument for use as a measure of self-reported health status. The EQ-5D comprises 5 dimensions (mobility, self-care, usual activities, pain/discomfort and anxiety) and a visual analog rating scale (VAS). The utility data generated from the EQ-5D is recommended for and commonly used in cost effectiveness analysis.

The EQ-5D will be administered along with the EORTC QLQ-C30 during on-study phases (Parts 1 and 2) as outlined in [Section 5.1](#), to all subjects.

Healthcare resource utilization data (eg, hospitalizations, non-protocol specified medical visits, diagnostics, etc) will be collected for all randomized subjects. The resource utilization capture is specific to hospital admission utilization data and non-protocol specified visits related to study therapy. Resource utilization questions will be collected on-study phases (Parts 1 and 2) as outlined in [Section 5.1](#), to all subjects.

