Review of Concomitant Medications	X	
Laboratory Tests	X	Within 72 hrs prior to dosing to include CBC w/ differential, LFTs, BUN or serum urea level, creatinine, Ca, Mg, Na, K, Cl, LDH, Glucose, amylase, lipase, TSH (+ reflex Free T4 and Free T3), albumin if clinically indicated).
Pregnancy Test (WOCBP only)	X	Serum or urine within 24 hours prior to administration of first dose and every 3 weeks thereafter in Part 1 of the study.
Pharmacokinetic and Immunogenicity Assessments		
Immunogenicity blood sample	See Section 5.5 for details regarding specific sample timing	
PK Samples	See Section 5.5 for details regarding specific sample timing	

Table 5.1-2: On-Study Assessments Part 1 (CA209511)		
Procedure	For Part 1, Study Drug Every 3 Weeks for 4 Cycles (Both Arm A and Arm B)	Notes
	Cycle 1, 2, 3, 4 (Day 1)	
Exploratory Biomarker Testing		
Exploratory Serum Biomarkers	X	To be collected pre-dose; before first 4 combination doses only.
Peripheral Blood Mononuclear Cells (PBMCs)	X	To be collected pre-dose; before first 4 combination doses only. To be collected in USA and Canada only.
Whole Blood Sample (DNA)	X	X = before first combination dose only.
Myeloid-Derived Suppressor Cell (MDSCs)	X	To be collected pre-dose; before the first and the third combination dose only
Efficacy Assessment		
Tumor Assessment	See Notes	FIRST tumor assessment should be performed at 12 weeks (\pm 1 wk) following randomization. CT Chest, CT (or MRI) abdomen, pelvis and all known sites of disease. Use same imaging method as was used at screening/baseline. Subjects with a history of brain metastasis should have surveillance MRI approximately every 12 weeks, or sooner if clinically indicated

Table 5.1-2: On-Study Assessments Part 1 (CA209511)		
Procedure	For Part 1, Study Drug Every 3 Weeks for 4 Cycles (Both Arm A and Arm B)	Notes
	Cycle 1, 2, 3, 4 (Day 1)	
Outcomes Research Assessments		
EORTC QLQ-C30 and EQ-5D	X	To be completed at the start of the clinic visit every 6 weeks. First questionnaire should be completed after IRT randomization but before dosing. (Cycle 1, 3)
Health Care Utilization	X	Health Care Utilization will be collected at each visit
Clinical Drug Supplies		
IRT Drug Vial Assignment	X	Within 24 hours prior to dosing
Administer Study Treatment	X	First dose to be administered within 3 days following randomization. See Section 4.3 .

Table 5.1-3: On-Study Assessments - Part 2 (CA209511)		

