Procedure	For Part 2, Study Drug is Administered Every 4 Weeks (Both Arm A and Arm B)	Notes Cycle 5 will begin 6 weeks after Cycle 4
	Cycle 5 and beyond (Day 1)	
Safety Assessments		
Targeted Physical Examination	X	To be performed only if clinically indicated within 72 hours prior to dosing
Vital Signs	X	Including BP, HR, temperature (Section 5.3)
Physical Measurements (including performance status)	X	Weight and ECOG Performance status within 72 hours prior to dosing
Adverse Events Assessment	Continuously	
Review of Concomitant Medications	X	
Laboratory Tests	X	Beginning at Cycle 5 and every alternate dose thereafter (Cycle 7, 9, 11, 13, etc), on-study local laboratory assessments should be done within 72 hours prior to the first (Part 2) dose and include: CBC w/differential, LFTs (ALT, AST, total bilirubin, alkaline phosphatase), BUN or serum urea level, creatinine, Ca, Mg, Na, K, Cl, LDH, glucose, amylase, lipase, TSH with reflexive Free T4, Free T3. (Albumin if clinically indicated) Beginning at Cycle 6 and every alternate dose thereafter (Cycle 8, 10, 12, 14, etc), on-study local laboratory assessment should be done within 72 hours prior to the second (Part 2) dose and include: LFTs (ALT, AST, total bilirubin, alkaline phosphatase) and creatinine.
Pregnancy Test (WOCBP only)	X	Serum or urine within 24 hours prior to first dose and every 4 weeks thereafter in Part 2

Table 5.1-3: On-Study Assessments - Part 2 (CA209511)		
Procedure	For Part 2, Study Drug is Administered Every 4 Weeks (Both Arm A and Arm B)	Notes Cycle 5 will begin 6 weeks after Cycle 4
	Cycle 5 and beyond (Day 1)	
Outcomes Research Assessments		
EORTC QLQ-C30 and EQ-5D	X	To be completed at the start of the clinic visit every 4 weeks from Cycles 5 to 11
Health Care Utilization		Health Care Utilization will be collected at each visit
Pharmacokinetic and Immunogenicity Assessments		
Immunogenicity blood sample	See Section 5.5 for details regarding specific sample timing	
PK Samples	See Section 5.5 for details regarding specific sample timing	
Efficacy Assessment		

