Tumor Assessments	See Notes		
Only for subjects without progression on study therapy.
 
FIRST tumor assessment should first be performed at 12 weeks (± 1 wk) following randomization
 
SUBSEQUENT tumor assessments should occur every 8 weeks (± 1 wk) thereafter for the first 12 months, then every 12 wks (± 2 wk) until disease progression
 
CT Chest, CT (or MRI) abdomen, pelvis and all known sites of disease. Use same imaging method as was used at screening/baseline.
 
Subjects with a history of brain metastasis should have surveillance MRI approximately every 12 weeks, or sooner if clinically indicated

Exploratory Biomarker Testing			
Tumor Tissue Biopsy	X	X	Optional; collection upon progression

^a X visits occur as follows - X1 = 30 days from the last dose (± 7 days) or coincide with the date of discontinuation (± 7 days) if date of discontinuation is greater than 37 days after last dose, X2 = 84 days (± 7 days) from follow-up visit 1. Follow up visits X1 and X2 will occur only after patient completes all study treatment.

^b Y Survival visits = every 3 months from X2 (± 7 days).

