8 STATISTICAL CONSIDERATIONS

8.1 Sample Size Determination

Approximately 346 subjects will be randomized to the 2 treatment arms in a 1:1 ratio in order to target 340 treated subjects (170 per arm). Given a two-sided alpha of 0.05, this number of treated subjects provides 80% power to show a statistically significant difference in the rate of drug-related Grade 3 - 5 AEs between the two treatment arms, assuming a rate of 40% in Arm A and a rate of 55% in Arm B.

We assume that treatment with N3I1 (Arm A) will result in a 15% reduction in the rate of drug-related Grade 3 - 5 events when compared to treatment with N1I3 (Arm B). The difference of 15% is clinically meaningful and assumes a 40% event rate in Arm A and a 55% event rate in Arm B. The assumption of 55% in Arm B is based on observed rates of drug-related Grade 3 - 5 AEs in the combination arm of studies CA209069 and CA209067, which enrolled the same patient population as the current study (previously untreated metastatic melanoma). The assumed reduction to 40% in Arm A corresponds to the same rate ratio (0.727) that was observed in Cohort 2a relative to Cohort 2 in Study CA209004.

Table 8.1-1 shows the precision that the sample size of 170 treated subjects per arm will provide for estimating adverse event rates (primary endpoint) or objective response rates (secondary endpoint), under different assumed observed rates.

For example, if exactly 68 of 170 treated subjects (40%) experience a drug-related Grade 3 - 5 AE in Arm A and 94 of 170 treated subjects (55.3%) experience a drug-related Grade 3 - 5 AE in Arm B, then the exact 95% CI for the rate of drug-related Grade 3 - 5 AEs will be (32.6%, 47.8%) for Arm A and (47.5%, 62.9%) for Arm B.

Furthermore, if exactly 102 of 170 treated subjects (60%) experience an objective response in a treatment arm, then the exact 95% CI for the ORR in that treatment arm will be (52.2%, 67.4%). If the observed ORR is exactly the same in each arm and equal to 60%, then the 95% CI for the difference in ORR between arms will be (-10.4%, 10.4%), and the 95% CI for the odds ratio will be (0.65, 1.54).

Table 8.1-1: Exact 95% CI for Rates when Observed in 170 Subjects			
Number Subjects with Event	Observed Rate	Lower limit Exact 95% CI	Upper limit Exact 95% CI
68	40.0%	32.6%	47.8%
77	45.3%	37.7%	53.1%
85	50.0%	42.2%	57.8%
94	55.3%	47.5%	62.9%
102	60.0%	52.2%	67.4%

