8.4.7 Outcomes Research Analyses

Analysis of EORTC QLQ-C30 will be performed in all patients who have an assessment at baseline and at least one follow-up assessment. All scales and single items are scored on a categorical scale and linearly transformed to 0-to-100 scales with higher scores for a functional scale representing higher levels of functioning, higher scores for the global health status/quality of life representing higher levels of global health/quality of life and higher scores for a symptom scale representing higher level of symptoms. EORTC QLQ-C30 scale data will be summarized by timepoint using descriptive statistics for each treatment group

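### No quality-of-life form is scheduled after study drug stops, so the by-timepoint HRQoL means describe subjects still on drug, and the loss is likely to differ between the arms

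*Protocol*

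**What the plan says.** **Collection.** Protocol Section 5.7 limits the questionnaires to the treatment period: "The EQ-5D will be administered along with the EORTC QLQ-C30 during on-study phases (Parts 1 and 2) as outlined in" Section 5.1. For Part 1, Table 5.1-2 states: "First questionnaire should be completed after IRT randomization but before dosing. (Cycle 1, 3"). For Part 2, Table 5.1-3 states: "To be completed at the start of the clinic visit every 4 weeks from Cycles 5 to 11".

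**After stopping.** Under Section 3.1.3 follow-up begins once it is decided to stop study therapy. Table 5.1-4 covers that phase with visits X1 (30 days from last dose) and X2 (84 days after X1), and its footnote says: "Follow up visits X1 and X2 will occur only after patient completes all study treatment". The table has no outcomes-research row. Section 3.5 sends subjects who discontinue to the Section 5 procedures, which schedule no form for them.

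**Analysis.** Section 8.3.2 measures HRQoL by mean change from baseline. Section 8.4.7 sets the analysis population: "Analysis of EORTC QLQ-C30 will be performed in all patients who have an assessment at baseline and at least one follow-up assessment". The summaries are descriptive, by timepoint and arm. SAP Section 7.9.2 applies the same population rule to EQ-5D.

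**Two statements that do not fit the tables.** The SAP 7.9.2 completion rate counts subjects in follow-up among those expected to return an EQ-5D form. Protocol Section 3.1.2 describes forms every 6 weeks for 6 months and then every 4 weeks to about Week 40, which does not match Cycles 1, 3 and 5 to 11.

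**The concern.** The two regimens are chosen because they are expected to differ in toxicity, and HRQoL is one place where a subject would feel that difference. Yet a subject who stops drug because of toxicity is not asked to complete a questionnaire again. The forms are lost partly through the effect the trial is built to show, and the loss is expected to be larger in the more toxic arm.

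The stake is how the HRQoL tables are read. At each later timepoint they describe subjects who were still being dosed, not the treated population. If stoppers feel worse than those who continue, both arms look better than they are, and Arm B probably more so. No analysis method can recover forms that were never collected.

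**Working it through.** **1. The planning figure that supplies the toxicity gap.** The documents give no figure for HRQoL. For the primary endpoint, Section 8.1 plans allocation "in a 1:1 ratio in order to target 340 treated subjects (170 per arm"), states "Given a two-sided alpha of 0.05, this number of treated subjects provides 80% power", and does so "assuming a rate of 40% in Arm A and a rate of 55% in Arm B". Check with unpooled variance: SE = sqrt[(0.40 x 0.60 + 0.55 x 0.45)/170] = sqrt(0.4875/170) = 0.0536; 0.15/0.0536 - 1.96 = 0.84; power = 80.0%. Pooled variance gives 79.4%. The stated power reproduces, so 40% vs 55% is used below as the trial's own toxicity assumption.

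**2. When forms fall.** Using the stated intervals (3-weekly cycles, Cycle 5 six weeks after Cycle 4, then 4-weekly):

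| Cycle | 1 | 2 | 3 | 4 | 5 | 6 | ... | 11 |
|---|---|---|---|---|---|---|---|---|
| Week | 0 | 3 | 6 | 9 | 15 | 19 | ... | 39 |
| Form | yes | no | yes | no | yes | yes | yes | yes |

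That is 2 + 7 = 9 forms at most, 8 of them post-baseline. By the tables none falls between Week 6 and Week 15. (Section 5.3 labels Cycle 5 as Week 18 and a footnote to Table 5.5.1-1 as Week 16; either would lengthen the gap.)

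**3. What happens to subjects who stop.**
- No Cycle 3 form: no post-baseline form, so excluded by Section 8.4.7.
- Stop between the Cycle 3 form and Cycle 5: kept, with only the Week 6 form, completed before stopping.
- Stop in Part 2: kept up to the last treatment visit with a form, then absent.

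**4. Link to toxicity.** Section 4.4.4 requires permanent discontinuation for many drug-related Grade 3 events and most Grade 4 events, with listed exceptions. The primary endpoint and the loss of forms are therefore connected by protocol rule.

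**5. Size.** The documents give no stopping rate, timing or HRQoL deficit. Assume:
- s = share of subjects with a drug-related Grade 3-5 AE who stop drug, 30-70%;
- d = points by which stoppers would score worse than those continuing, 5-20;
- s and d equal in both arms, no other cause of loss, and a timepoint by which these stops have occurred.

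The full-arm mean is the on-drug mean minus (AE rate x s x d), so the on-drug mean is too favourable by that product.

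| | Arm A | Arm B |
|---|---|---|
| Stoppers of 170, s = 30% | 170 x 0.40 x 0.30 = 20 | 170 x 0.55 x 0.30 = 28 |
| Stoppers of 170, s = 50% | 34 | 47 |
| Stoppers of 170, s = 70% | 48 | 65 |
| Mean too favourable, s = 30%, d = 5 | 0.6 | 0.8 |
| Mean too favourable, s = 70%, d = 20 | 5.6 | 7.7 |

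Hidden between-arm difference = (0.55 - 0.40) x s x d: from 0.15 x 0.30 x 5 = 0.2 to 0.15 x 0.70 x 20 = 2.1 points.

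If 20-60% of stoppers stop before Cycle 3 (also an assumption), those excluded entirely number 4-12 in Arm A and 6-17 in Arm B at s = 30%, and 10-29 and 13-39 at s = 70%.

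**6. Direction.** With unequal s or d, the sign reverses if s x d in Arm A exceeds that in Arm B by more than 0.55/0.40 = 1.375. Progression also ends treatment. If those who stop for progression have the same deficit d, an excess of 0.15 x s (4.5 to 10.5 percentage points) of progression stops in Arm A would cancel the toxicity effect.

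**The case against.** **HRQoL is only described.** The objective is to evaluate it, SAP Section 7.1 confines formal testing to the primary endpoint, and the available text plans no between-arm HRQoL test, margin or power. This stands. A reader might infer that the trial is set up to conclude wrongly that HRQoL does not differ; the documents plan no such conclusion.

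**Most stoppers are not removed.** A reader might infer that everyone who stops for toxicity leaves the HRQoL analysis. Only those without a Cycle 3 form do. Forms are completed at the start of the visit, so a subject taken off drug at the Cycle 3 visit may still have one. The rest remain, with pre-stop forms.

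**Section 4.4.4 is not a blanket stop.** Shorter non-recurrent Grade 3 non-skin events outside the named types, controlled endocrinopathies other than adrenal insufficiency, and most Grade 3 laboratory abnormalities do not automatically end treatment. This is why s is shown as a range.

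**The SAP may deal with it.** Its contents list QLQ-C30 time windows (Tables 4.2.4-1 and 4.2.4-2) and a QLQ-C30 analysis section (7.9.1). Sections 4.2.4 and 7.9.1 were not in the text available for this review, so their handling of missing forms cannot be judged. The EQ-5D denominator suggests that someone expected forms in follow-up. Neither changes the protocol schedule.

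**Hospital admissions after stopping are not lost to the trial.** Serious adverse events are collected for 100 days. The treatment-period limit on healthcare-utilization data is therefore a secondary matter.

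**Conclusion.** The point holds as a gap in data collection with a modest, uncertain effect on interpretation. No QLQ-C30 or EQ-5D form is scheduled after study drug stops, and the analysis rule drops subjects with no Cycle 3 form. The by-timepoint means are therefore on-drug means.

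Given the 40% vs 55% assumption, the loss is expected to be larger in Arm B and would probably understate any HRQoL advantage of Arm A. Under the assumptions in the working, 0.2-2.1 points of between-arm difference are hidden, while each arm's own later means are too favourable by 0.6-5.6 (A) and 0.8-7.7 points (B). These figures rest on assumed stopping shares and deficits, equal across arms, and on toxicity as the only cause of loss.

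Two stronger readings are not supported. Bias toward no difference is likely but not certain, because progression also stops treatment and the deficit may differ by arm. A loss as large as 4 points (0.20 x 20) needs a 20-point gap in stopping rates, which exceeds the trial's own 15-point gap in drug-related Grade 3-5 events. Type I error and the primary endpoint are not affected.

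**What to change.** - **Schedule.** Add an outcomes-research row to Table 5.1-4 with QLQ-C30 and EQ-5D at X1 and X2 for every treated subject, whatever the reason for stopping, and amend Section 5.7 to match.
- **Analysis.** X1 and X2 are timed from last dose, so assign these forms to windows by time since baseline. After a last dose at Week 3 they fall near Weeks 7 and 19 (3 + 30/7, then + 84/7); after a last dose at Week 9, near Weeks 13 and 25. Summarize by arm and by on/off-treatment status.
- **Completion.** Report completion by arm and timepoint, with treated subjects still alive as the denominator.
- **Reconcile.** Bring the SAP 7.9.2 EQ-5D denominator and the questionnaire schedule in protocol Section 3.1.2 into line with Tables 5.1-2 to 5.1-4.
- **Optional.** Add forms at the existing Cycle 2 and Cycle 4 visits, and healthcare-utilization questions at X1 and X2.

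**Cost.** A schedule amendment and extra rows in the SAP tables. No new visit is needed: X1 and X2 exist, and Section 5.3 already asks for in-person toxicity assessment in safety follow-up. The downside is a small questionnaire burden at two visits and some forms missing from unwell subjects. The repair is partial: it reaches about 114 days (30 + 84) after last dose, so early stoppers remain absent from the latest timepoints, and the report should say so.
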